2.3. Benefit/Risk Assessment

Ritlecitinib (PF-06651600) is not expected to provide any clinical benefit to healthy participants of this study. This study is designed primarily to generate PK data for further JAK3 development. In this study, ritlecitinib (PF-06651600) will be administered at single doses of 30 mg.

Ritlecitinib (PF-06651600) was determined to be well tolerated and to have an acceptable safety profile in the clinical studies. Reductions in platelet counts and lymphocyte counts were observed during treatment with 200 mg QD, but were not considered clinically meaningful and improved after switching to 50 mg QD. Ritlecitinib (PF-06651600) is an immunomodulator and, as such, can be associated with the potential risk of infections (including serious infections), opportunistic infections, and viral reactivation. The risk of

infection will be monitored in this study and evaluated in longer term studies of ritlecitinib (PF-06651600).

In animals, ritlecitinib (PF-06651600) was associated with fetal changes in bones and some internal organs, and lower fetal body weights. It is not known whether ritlecitinib (PF-06651600) is secreted into human milk. Because of that and because of the investigational nature of ritlecitinib (PF-06651600), it should not be administered to pregnant women, breastfeeding women, or fertile WOCBP who are unwilling or unable to use contraception as defined in the study protocol. Men in the study are not required to use birth control, because ritlecitinib (PF-06651600) is not likely to transfer to a partner through semen at pharmacologically relevant blood levels.

More detailed information about the known and expected benefits and risks and reasonably expected adverse events of ritlecitinib (PF-06651600) may be found in the IB, which is SRSD for this study.

Overall, single doses of ritlecitinib (PF-06651600) of 30 mg in healthy participants are expected to be safe and well tolerated in this study.

2.3.1. Risk Assessment

Potential Risk of Clinical Significance	Summary of Data/Rationale for Risk	Mitigation Strategy
Study Intervention ritlecitinib (PF-06651600)		
Reductions in platelet counts and lymphocyte counts.	In B7931005 study, reductions in platelet counts and lymphocyte counts were observed during treatment with 200 mg QD, but were not considered clinically meaningful and improved after switching to 50 mg QD.	Clinical laboratory results will be monitored.
Potential risk of infections.	Ritlecitinib (PF-06651600) is an immunomodulator and, as such, can be associated with the potential risk of infections (including serious infections), opportunistic infections, and viral reactivation.	Participants with infection history will be excluded (See Section 5.2) and the risk of infection will be monitored in the study.
Potential fetal risk.	In animals, ritlecitinib (PF-06651600) was associated with fetal changes in bones and some internal organs, and lower fetal body weights. When male rats were treated with ritlecitinib (PF-06651600) and mated with female rats that	WOCBP who are unwilling or unable to use contraception as defined in the study protocol will be excluded (See Section 5.3.4 and Appendix 4).

PFIZER CONFIDENTIAL

Potential Risk of Clinical Significance	Summary of Data/Rationale for Risk	Mitigation Strategy
Study Intervention ritlecitinib (PF-06651600)		
	were not treated, there were smaller litter sizes due to fewer fertilized eggs attaching to the wall of the uterus in those female rats. There were no effects on sperm or other features of male reproduction.	
Potential risk of secreting into human milk.	It is not known whether ritlecitinib (PF-06651600) is secreted into human milk.	Ritlecitinib (PF-06651600) should not be administered to breastfeeding women and exposure during breastfeeding should be reported to Pfizer Safety (See Section 8.3.5.2).

3. OBJECTIVES AND ENDPOINTS

Objectives	Endpoints
Primary: 
To estimate the relative BA of ritlecitinib (PF-06651600) pediatric capsules (3×10 mg capsule, Test) relative to adult 30 mg capsule (Reference) under fasted conditions in healthy adult participants.To estimate the relative BA of ritlecitinib (PF-06651600) administered as 30 mg spray congealed beads (Test) relative to adult 30 mg capsule (Reference) under fasted conditions in healthy adult participants.	Primary: 
Plasma AUC_{inf} and C_{max} for ritlecitinib (PF-06651600).
Secondary: 
To evaluate the safety and tolerability of 10 mg capsules, 30 mg capsules and spray congealed beads at the 30 mg dose of ritlecitinib (PF-06651600) administered to healthy adult participants under fasted conditions.	Secondary: 
Safety laboratory tests and AE monitoring.
Other: 
To characterize the PK of ritlecitinib (PF-06651600) administered as pediatric capsules (3×10 mg capsule), adult 30 mg capsule and 30 mg spray congealed beads in healthy adult participants under fasted conditions.To assess the sensory characteristics and overall palatability of spray congealed beads by healthy participants.	Other: 
T_{max}, AUC_{last}, $t_{1/2}$ (if data permit) and other PK parameters such as CL/F, V_z/F.Responses to the taste assessment questionnaire that document overall liking, mouth feel, bitterness, sourness, saltiness and tongue/mouth burn of sensory attributes.

4. STUDY DESIGN

4.1. Overall Design

The study will be conducted as a Phase 1, open-label, single dose, randomized, 3 period, cross-over design in a single cohort of approximately 12 healthy male or female participants at a single center. Participants will be randomized into 2 sequences of treatment as described in [Table 2](#):

Sequence 1 (n=6): A B C

Sequence 2 (n=6): B A C

Table 2. Study Design and Treatments

Treatment Sequence	Period 1	Washout	Period 2	Washout	Period 3
1 (n=6)	A	At least 2 days of washout between dosing	B	At least 2 days of washout between dosing	C
2 (n=6)	B		A		C

n = number of participants.

Treatment A: ritlecitinib (PF-06651600) 30 mg intact adult capsule

Treatment B: ritlecitinib (PF-06651600) 3 × 10 mg pediatric capsules

Treatment C: ritlecitinib (PF-06651600) 30 mg spray congealed beads

Since ritlecitinib (PF-06651600) is rapidly eliminated ($t_{1/2} \sim 2$ hours), there will be at least a 48-hour washout between each dose.

Blood samples for PK analysis will be collected pre-dose and at 0.25, 0.5, 1, 1.5, 2, 3, 4, 6, 9, 12, 16 and 24 hours post-dose.

Participants will participate in the study up to approximately 2.5 months, including the screening and follow-up periods. Participants will be screened within 28 days of the first dose of study intervention and if all entry criteria are fulfilled, the participants will report to the CRU on the day prior to Period 1 Day 1 dosing (Day -1). On Day 1 of each period, participants will receive a single dose of study intervention. Capsules and spray congealed beads will be administered with approximately 240 mL of ambient temperature water, and will be swallowed (not chewed). Participants will be fasted for at least 10 hours pre-dosing and 4 hours post-dosing.

For the taste assessment in Period 3, participants will be asked to not verbalize their responses and not discuss taste with other participants until after they have filled out the responses in the questionnaire.

Participants will be confined in the CRU for a total of at least 7 days (6 nights which includes admission to the CRU on Day -1) and discharged at the discretion of the investigator. A follow-up phone call will be made at least 28 calendar days and up to 35 calendar days after the last administration of the study interventions to capture any potential AE and confirm appropriate contraceptive usage.

Participants who withdraw from the study may be replaced at the discretion of the sponsor.

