- n. If not collected on the designated collection day, collect at the next available time point when biospecimens are being collected in conjunction with a participant visit.
- o. Collected at pre-dose.
- p. Dosing of each period to be separated by at least a 48-hour washout interval. The participants will be discharged on Day 2 of Period 3.
- q. Review taste assessment questionnaire and instructions with participants prior to dosing in Period 3, Day 1. Each participant will record the sensory attributes at timed intervals of 0 (immediately after dosing), 5, 10 and 20 minutes after administration using a taste assessment questionnaire (see [Appendix 9](#)).

Table 1. Pharmacokinetic Sampling Schema for Period 1, Period 2 and Period 3

Visit Identifier	Period 1, Period 2 and Period 3												2
	1												
Study Day	0 ^a	0.25	0.5	1	1.5	2	3	4	6	9	12	16	24
Hours Before/After Dose	X												
Study Intervention Administration	X												
Ritlecitinib (PF-06651600) PK blood sampling ^b	X	X	X	X	X	X	X	X	X	X	X	X	X

a. Predose PK samples. Any time prior to dosing ritlecitinib (PF-06651600) on the day of dosing.

b. Ritlecitinib (PF-06651600) PK blood samples (2 mL blood to yield approximately 0.5 mL plasma) are to be collected.

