8.11. Taste Assessment

Taste assessment of the spray congealed beads will be conducted in Period 3 with the aid of a questionnaire ([Appendix 9](#)). The taste assessment questionnaire will be administered to participants by trained staff using a colored copy of the questionnaire. Participants after drug administration will be asked to rate the overall liking, mouth feel, bitterness, sourness, saltiness and tongue/mouth burn. The participants will rate the above immediately after dosing and at 5 min, 10 min, 20 min after dosing.

See [Appendix 9](#) for the details about the taste assessment questionnaire.

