9.1. Statistical Hypotheses

No statistical hypothesis will be tested in this study.

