To estimate the relative BA of ritlecitinib (PF-06651600) pediatric capsule (3×10 mg capsules) relative to adult 30 mg capsule, the natural log transformed AUC_{inf} (if data permit), AUC_{last} and C_{max} will be analyzed using a mixed effects model with sequence, period and treatment as fixed effects and participant within sequence as a random effect. Estimates of the adjusted mean differences (Test-Reference) and corresponding 90% confidence intervals will be obtained from the model. The adjusted mean differences and 90% confidence intervals for the differences will be exponentiated to provide estimates of the ratio of adjusted geometric means (Test/Reference) and 90% confidence intervals for the ratios. Treatment A (30 mg capsule form of ritlecitinib [PF-06651600] under fasted conditions) will be the Reference treatment while Treatment B (3×10 mg pediatric capsules of ritlecitinib [PF-06651600] under fasted conditions) will be the Test treatment. Data from Period 3 (Treatment C) will be excluded from this analysis.

To estimate the relative BA of ritlecitinib (PF-06651600) administered as 30 mg spray congealed beads (Test) relative to adult 30 mg capsule (Reference) under fasted conditions, the natural log transformed AUC_{inf} (if data permit), AUC_{last} and C_{max} will be analyzed using a mixed effects model with sequence and treatment as fixed effects and participant within sequence as a random effect. Estimates of the adjusted mean differences (Test-Reference) and corresponding 90% confidence intervals will be obtained from the model. The adjusted mean differences and 90% confidence intervals for the differences will be exponentiated to provide estimates of the ratio of adjusted geometric means (Test/Reference) and 90% confidence intervals for the ratios. Treatment A (30 mg capsule of ritlecitinib

[PF-06651600] under fasted conditions) will be the Reference treatment while Treatment C (30 mg spray congealed beads of ritlecitinib [PF-06651600] under fasted conditions) will be the Test treatment.

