## 10. APPENDICES

### Appendix 1. SAS CODE FOR ANALYSES

An example of the PROC MIXED code is provided below:

Comparison of Treatment A (intact adult capsule) and B ( $3 \times 10$  mg pediatric capsules);

```
proc mixed data=tab.pk;
  where period<3;
  class seq period trt subject;
  model l&var=seq period trt/ ddfm=KR;
  random subject(seq) /subject=subject(seq);
  lsmeans trt;
  estimate Treatment B vs Reference (A)' trt -1 1 /cl alpha=0.1;
  ods 'Estimates' out=est&var;
  ods 'lsmeans' out=ls&var;
  ods 'covparms' out=cov&var;
  ods 'tests3' out=tst&var;
run;
```

/\* Letter assignments for treatments (trt) within the estimate statement above are as follows;  
Treatment A: ritlecitinib (PF-06651600) 30 mg intact adult capsule (reference);  
Treatment B: ritlecitinib (PF-06651600)  $3 \times 10$  mg pediatric capsules (test);\*/

Comparison of Treatment A (intact adult capsule) and C (spray congealed beads);  
Treatment B (pediatric capsule) excluded

```
proc mixed data=tab.pk;
  where trt in ("A" "C");
  class seq trt subject;
  model l&var=seq trt/ ddfm=KR;
  random subject(seq) /subject=subject(seq);
  lsmeans trt;
  estimate Treatment C vs Reference (A)' trt -1 1 /cl alpha=0.1;
  ods 'Estimates' out=est&var;
  ods 'lsmeans' out=ls&var;
  ods 'covparms' out=cov&var;
  ods 'tests3' out=tst&var;
run;
```

/\* Letter assignments for treatments (trt) within the estimate statement above are as follows;  
Treatment A: ritlecitinib (PF-06651600) 30 mg intact adult capsule (reference);  
Treatment C: ritlecitinib (PF-06651600) 30 mg spray congealed beads (test); \*/

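### Beads are given last to everyone, so the second primary ratio (beads/adult capsule) cannot be separated from a Period 3 effect

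*Protocol*

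**What the plan says.** Protocol Section 4.1 (Table 2) and SAP Section 2.1 give two sequences of six participants, ABC and BAC ("Sequence 2 (n=6): B A C"). Only the order of A and B is randomised.

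Protocol Section 3 lists two primary objectives, with AUCinf and Cmax as endpoints. The second is "To estimate the relative BA of ritlecitinib (PF-06651600) administered as 30 mg spray congealed beads (Test) relative to adult 30 mg capsule (Reference").

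The two comparisons are modelled differently (Protocol Section 9.4.3, SAP Section 8.2.1):

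- **B/A:** sequence, period and treatment are fixed effects. "Data from Period 3 (Treatment C) will be excluded from this analysis".
- **C/A:** a "mixed effects model with sequence and treatment as fixed effects and participant within sequence as a random effect". There is no period term. The SAP Appendix 1 code agrees: "model l&var=seq trt/ ddfm=KR".

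Protocol Section 4.2 gives no reason for placing C last. Neither document says that C/A rests on an assumption of no period effect, and neither plans a sensitivity analysis for one.

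**The concern.** A crossover protects a treatment contrast from time effects because each treatment appears in each period. Here that protection covers A against B but not C against A. Anything that makes the third dosing occasion differ from the first two passes in full into the beads/adult-capsule ratio, and the 90% interval carries no allowance for it.

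The issue is a period effect, not carryover. The Schedule of Activities requires: "Dosing of each period to be separated by at least a 48-hour washout interval". With a half-life of about 2 hours, 48 hours is 24 half-lives, leaving a residual fraction of 2^-24, about 6e-8.

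The trial is for estimation only ("No statistical hypothesis will be tested in this study"), so no formal test is at risk. The estimate and its interval are the whole result, and what is at stake is how far they can be trusted.

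**Working it through.** **Inputs.** Within-subject SDs on the log scale are 0.106 (AUCinf) and 0.212 (Cmax), with n = 12 and 90% intervals (Protocol Section 9.2). The sequences are ABC and BAC, six each (Section 4.1). The documents give no period-effect size, so every shift below is an assumption.

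**The plan's own figure.** SE(ln ratio) = SD × √(2/12):

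- AUC: 0.106 × 0.4082 = 0.0433
- Cmax: 0.212 × 0.4082 = 0.0865

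The Section 9.2 intervals are reproduced by ratio × exp(± t(0.95, 10) × SE × √(χ²(0.90, 10)/10)), with t = 1.812 and the last factor 1.264. At a ratio of 100% this gives 90.6-110.4% (AUC) and 82.0-121.9% (Cmax), as printed. The factor 1.264 is a 90% tolerance allowance that the plan does not state. The limits used below omit it and are therefore narrower.

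**Estimability.** Take the model with participant, period and treatment for 12 participants. It has 16 columns: 12 participants, 2 periods, 2 treatments. The Period 3 and Treatment C columns are identical, so the rank is 15. B-A is estimable; C-A is not, whether in the joint model or in the A and C data alone. Leaving period out of the C/A model is therefore forced by the design and is not a coding error.

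**What the planned C/A model estimates.** In ABC, C minus A carries P3 - P1. In BAC it carries P3 - P2. With six in each sequence:

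E[estimate] = (C - A) + P3 - (P1 + P2)/2

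Check with a true C - A of 0 and log-scale period effects (0, 0.06, 0.10): 0.10 - 0.03 = 0.07, which is what least squares returns. With unequal completers only the weights change. For 6 and 4 the bias is 0.10 - (6×0 + 4×0.06)/10 = 0.076, and the aliasing is still complete.

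**Size.** The C/A model has 24 - 12 - 1 = 11 residual df. Coverage comes from the noncentral t distribution with 11 df and noncentrality ln(1 + shift)/SE. For example, a 5% shift for AUC gives 0.0488/0.0433 = 1.13.

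| Assumed Period 3 shift relative to the mean of Periods 1-2 | AUC coverage | Cmax coverage |
|---|---|---|
| +1% | 89% | 90% |
| +2% | 87% | 89% |
| +3% | 83% | 88% |
| +5% | 72% | 85% |
| +10% | 34% | 73% |
| -5% | 70% | 85% |
| -10% | 26% | 69% |

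For upward shifts, coverage falls below 85% at about 2.5% (AUC) or 5.2% (Cmax), and below 80% at about 3.6% or 7.4%.

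**Can the trial rule such shifts out?** The A/B model estimates Period 2 against Period 1 with 10 df. At no effect, its 90% limits are exp(± 1.812 × SE): -7.5% to +8.2% (AUC) and -14.5% to +17.0% (Cmax). A true 5% effect would be excluded from the null in only 28% (AUC) or 15% (Cmax) of trials. Nothing in that model measures Period 3.

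**The case against.** The other side has real points.

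- **No bias is shown, and conditions are tightly controlled.** Doses fall on Days 1, 3 and 5 of one confinement, with fasting, meals, posture, water volume and dosing time standardised (Protocol Sections 1.3, 5.3 and 6.1.1). This stands: a large period effect is less likely. It does not exclude one, no figure supports its absence, and the B/A model does adjust for period.
- **The beads are the secondary candidate.** The rationale text (Sections 1.1 and 2.1) names the 10 mg capsule comparison as the primary objective and introduces the beads as an alternative. The design fully protects that lead comparison. This limits the importance of the point. C/A is nevertheless listed as primary in Section 3 and is to be reported in the same form as B/A.
- **Half-life and the terminal rate constant are derived for every treatment, Period 3 included.** A change in clearance over time might show there. That is a fair indirect check, but it cannot reveal a period effect on absorption or Cmax, and the apparent half-life may itself depend on how the beads release drug.
- **Placing C last may suit the taste test.** "Taste assessment of the spray congealed beads will be conducted in Period 3 with the aid of a questionnaire" (Section 8.11). Neither document gives this as the reason. The SAP revision history lists only the taste objective and taste analysis as additions in version 2.0, which suggests that the order was set before taste was added.
- **Six orders leave only two participants per sequence, and replacement is discretionary.** Exact balance could be lost, but C would still be spread over periods. A three-sequence Latin square with four each would also remove the aliasing.

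**Conclusion.** The concern holds. C/A is completely aliased with Period 3 minus the mean of Periods 1 and 2 (equal weights for the planned 6/6 allocation), and no model contrast from the planned data can separate them. This follows from the design alone. How much harm results depends on a period effect the documents do not quantify: little at 1-2%, material for AUC from about 3%, and for Cmax from somewhat above 5%, taking the plan's SDs as correct and all 12 participants as completing. Bias is possible, not demonstrated. B/A is unaffected. The point should be fixed, because a primary ratio depends on an unstated and untestable assumption that the design can avoid cheaply.

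**What to change.** **Preferred.** Randomise the same 12 participants, two each, to ABC, ACB, BAC, BCA, CAB and CBA. Include period in both comparison models. Select data by treatment rather than by period in the B/A model and its code, since A or B could then fall in Period 3. Give the taste questionnaire in whichever period the beads are taken.

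**Precision.** The variance factor stays at 2/12. Pairwise models have 24 - 12 - 2 - 1 = 9 df (t = 1.833), against 10 now for B/A (1.812) and 11 for C/A (1.796). At a ratio of 1, the upper 90% limit for C/A moves from +8.1% to +8.3% (AUC) and from +16.8% to +17.2% (Cmax). A joint model has 36 - 12 - 2 - 2 = 20 df (t = 1.725), giving +7.7% and +16.1%, but assumes one residual variance for all three formulations.

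**Cost.** No extra participants, visits or samples. It needs a new randomisation schedule, beads available from Period 1 (the documents do not say whether this is feasible), and edits to the Schedule of Activities, the Period 3 taste wording and the SAP models. The real drawback is that a third of participants would taste in each period while confined together. The present request not to discuss taste lapses once a participant has completed the questionnaire, so it should run until everyone has finished tasting.

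**If C must stay last.** State in SAP Section 8.2.1 that C/A is a non-randomised, period-confounded estimate that assumes no period effect. Report the Period 2 versus Period 1 effect with its 90% interval from the A/B model beside it, and say that this is only indirect evidence about Period 3. Adding a period term to the current C/A model is not a remedy.

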4.2. Scientific Rationale for Study Design

A capsule formulation of the tosylate salt of ritlecitinib (PF-06651600) has been developed and nominated to be the marketed dosage form and is being evaluated in a pivotal BE trial relative to the tablets. The tablet formulation is the current clinical product at strengths of 10 mg and 50 mg. A 10 mg capsule and a spray congealed bead are being evaluated as potential candidate formulations for pediatric patients. Both these formulations have

qualitative and quantitative differences in their formulation excipients from the adult capsules.

The intent of the study is to estimate the relative bioavailability of ritlecitinib (PF-06651600) 10 mg capsule that is being developed as the market image/commercial pediatric drug product. An alternate dosage form, spray congealed beads, will also be evaluated for bioavailability relative to the adult 30 mg capsules. The spray congealed beads is being considered as an alternative pediatric formulation.

In an embryo-fetal development study in rats, skeletal malformations and variations and lower fetal body weights were observed at relevant clinical exposures for ritlecitinib (PF-06651600). In rabbits, lower mean fetal body weights and higher incidences of visceral and skeletal malformations and skeletal variations were observed at relevant clinical exposures for PF-06651600. See the IB for further details. Therefore, the use of a highly effective method of contraception is required in WOCBP (see [Appendix 4](#)).

The potential risk of exposure to ritlecitinib (PF-06651600) in a sexual partner of a male participant in this study via ejaculate is low, and therefore no contraception use in male participants is required. The calculated safety margin is ≥ 100 -fold between the estimated partner exposure due to seminal transfer and the NOAEL for serious manifestations of developmental toxicity in nonclinical studies. The safety margin of 100-fold is based on applying a 10-fold safety factor for interspecies extrapolation and a 10-fold safety factor for susceptible populations.¹

Banked Biospecimens will be collected and stored for further analyses which may, for example, provide greater understanding of the study intervention.

